End diastolic volume; Chi square test; Student t- test; Man, Whitney test; Level of significance < 0.05.

Table (10): Comparison between both groups as regard post intervention side effects

	Control group. (n= 41)	Study group. (n=38)	P value
AKI episodes No. (%)			
- No	38 (92.7%)	31 (81.6%) 5 (13.2%)	0.17
- once	1 (2.4%) 2 (4.9%)	2 (5.3%)	
- twice			
UTI No. (%)			
- No	35 (85.4%) 4 (9.8%)	31 (81.6%) 5 (13.2%)	0.8
- once	2 (4.9%)	2 (5.3%)	
- more than once			
Gynecological infection No. (%)	1 (2.4%)	2 (5.3%)	0.6
Viral infection No. (%)	1(2.4%)	1 (2.6%)	1
MMF intolerance No. (%)	1 (2.5%)	2 (5.3%)	0.6
Renal biopsy No. (%)	2 (4.9%)	1 (2.6%)	0.6
Increase steroid dose No. (%)	7 (17.1%)	4 (10.5%)	1

UTI: urinary tract infection episodes; AKI: acute kidney injury; chi-square test for categorical data. Categorical data are expressed as number (percentage).; Level of significance < 0.05.

figure1: flow chart of participating populations

Figure (2) shows difference between individual which had improved eGFR or not as regard to their basal eGFR in total cohort, which found that improving eGFR had been occurred in patients with lower eGFR (107±50 vs 137±58 ml/min/m²

Figure (3) show no significant difference between the drug and placebo groups (p=0.857). as regard incidence of anemia before intervention, the drug group has 23 anemic participants (60.5%) versus 24 participants (58.5%) in the placebo group, while post intervention, In the anemia category, the drug group has 16 participants (42.1%), while the placebo group has 22 participants (53.7%) with non-significant differences (p = 0.3)

Figure (4) differences in body weight between both groups at different time points:

Glossary of Terms and Abbreviations

AA	Amino Acids
ABIN	A20 Binding Inhibitor Of NF-Kb
ACE	Angiotensin-Converting Enzyme Inhibitors
ACR	American College of Rheumatology
AKI	Acute Kidney Injury
ALCAM	Activated Leucocyte Adhesion Molecule
ALP	Alkaline Phosphatase
AMP	Adenosine Monophosphate
АМРК	Amp-Activated Protein Kinase
ANA	Antinuclear Antibodies
ANG II	Angiotensin 2
ANOVA	Analysis Of Variance
ANTI-DSDNA	Anti Double Stranded Deoxyribonucleic Acid
	Antibodies
ANTI-SM	Anti-Smith Antibodies
APLS	Antiphospholipid Syndrome
ARBS	Angiotensin 2 Receptor Blockers
ATN	Acute Tubular Necrosis
ATP	Adenosine Triphosphate
BAFF	B-Cell-Activating Factor
BLISS	B Lymphocyte Stimulator Inhibitor Belimumab
	Plus Standard Therapy
BMI	Body Mass Index
BNP	Brain Natriuretic Peptide
BP	Blood Pressure
CAC	Coronary Artery Calcification
CAD	Coronary Artery Disease

САМК	Ca2+/Calmodulin-Dependent Protein Kinase	
CASR	Serine/Threonine Kinase Camk4	
CCS	Coronary Calcium Score	
CD163	Macrophage-Specific Protein	
CD4 T-CELLS	Helper T-Cells	
CD8 T-CELLS	Cytotoxic T-Cells	
CI	Confidence Interval	
CKD	Chronic Kidney Disease	
CKD-MBD	Chronic Kidney Disease-Mineral Bone Disorders	
CLD	Chronic Liver Disease	
CMV	Cytomegalovirus	
CNI	Calcineurin Inhibitors	
СТ	Computed Tomography	
CVD	Cardiovascular Disease	
CYC	Cyclophosphamide	
DAPA-HF	The Dapagliflozin and Prevention of Adverse	
	Outcomes in Heart Failure	
DCGF	Death-Censored Graft Failure	
DECLARE-TIMI 58	Dapagliflozin Effect on Cardiovascular Events-	
	Thrombolysis in Myocardial Infarction 58	
DELIGHT	Delay Of Impaired Glucose Tolerance by A	
	Healthy Lifestyle Trial	
DM	Diabetes Mellitus	
DNA	Deoxyribonucleic Acid	
EBV	Epstein Bar Virus	
EDV	End Diastolic Volume	
EF	Ejection Fraction	
EGFR	Estimated Glomerular Filtration Rate	
EMPA-REG	Empagliflozin-Removing Excess Glucose	

EPO	Erythropoietin	
EPOR	Erythropoietin Receptors	
ESRD	End-Stage Renal Disease	
ESV	End- Systolic Volume	
EULAR	The European League Against Rheumatism	
FDA	Food And Drug Administration	
FEUA	Fractional Excretion of Uric Acid	
FGF	Fibroblast Growth Factor	
FN1	Fibronectin 1	
GCS	Glucocorticoids	
H2 O2	Hydrogen Peroxide	
HBA1C	Glycated Hemoglobin	
HBV	Hepatitis B Virus	
HCV	Hepatitis C Virus	
HD	Hemodialysis	
HIF	Hypoxia-Inducible Factor	
HIV	Human Immunodeficiency Virus	
HLA	Human Leucocytic Antigen	
HPT	Hyperparathyroidism	
HR	Hazard Ratio	
HR-PQCT	High-Resolution Peripheral Quantitative	
	Computer Tomography	
HUS	Hemolytic Uremic Syndrome	
HZ	Herpes Zoster	
IFTA	Interstitial Fibrosis and Tubular Atrophy	
IGG	Immunoglobulin G	
IL-6	Interleukin-6	
IPTH	Intact Parathyroid Hormone	
ITP	Immune Thrombocytopenic Purpura	

KDIGO	Kidney Disease Improving Global Outcomes	
LAD	Left Atrial Dimension	
LDL	Low-Density Lipoprotein	
LUMINA	Lupus In Minorities; Nature Vs. Nurture	
LV	Left Ventricle	
МСН	Mean Corpuscular Hemoglobin	
MCP1	Monocyte Chemoattractant Protein-1	
MCV	Mean Corpuscular Volume	
MDCT	Multidetector CT	
MMF	Mycophenolate Mofetil	
MPAA	Mycophenolic Acid Analogue	
MRI	Magnetic Resonance Imaging	
NGAL	Neutrophil Gelatinase-Associated Lipocalin	
NH3	Na+/H+ Exchanger 3	
NHS	National Health Service	
NLR	Nucleotide-Binding Oligomerization Domain-	
	Like Receptor	
NSAIDS	Non-Steroidal Anti-Inflammatory Drugs	
PD	Peritoneal Dialysis	
PET	Positron Emission Tomography	
PGC-1A	Peroxisome Proliferators-Activated Receptor	
	Gamma Coactivator-1α	
QCT	Quantitative Computer Tomography	
RAAS	Renin-Angiotensin-Aldosterone	
RBG	Random Blood Glucose	
RCTS	Randomized Controlled Trials	
RNA	Ribonucleoside Antibodies	
ROS	Reactive Oxygen Species	

RPS/ISN	The Renal Pathology Society/International	
	Society of Nephrology	
RRT	Renal Replacement Therapy	
SBP	Systolic Blood Pressure	
SELENA-SLEDAI	Safety Of Estrogens in Lupus Erythematosus	
	National Assessment-SLE Disease Activity	
	Index	
SGLT2	Sodium-Glucose Cotransporter 2	
SGLT2 inhibitors	Sodium-Glucose Cotransporter 2 Inhibitors	
SIRT1	Sirtuin Type 1.	
SLE	Systemic Lupus Erythematosus	
SLEDAI	Systemic Lupus Erythematosus Disease Activity	
	Index	
SLICC	The Systemic Lupus International Collaborating	
	Clinics	
SNS	Sympathetic Nervous System	
T2DM	Type 2 Diabetes Mellitus	
TLRS	Toll-Like Receptors	
TNF	Tumor Necrosis Factor	
TSAT	Transferrin Saturation	
UTI	Urinary Tract Infection	
VCAM-1	Vascular Cell Adhesion Molecule-1

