Statistical Analysis Plan

Document Control

Title: Statistical Analysis Plan for the Study of SGLT2 Inhibitors in Lupus Nephritis Patients

Protocol ID: [NCT05748925] Version: 1.0 Date: [11/3/2024] Principal Investigator: [[name]] Statistician: [[name]] Approval Signatures: Principal Investigator: [name] Statistician: [name]

Table of Contents

- 1. Introduction
- 2. Study Design
- 3. Study Objectives
- 4. Endpoints
- 5. Sample Size Justification
- 6. Statistical Methods
- 7. Handling of Missing Data
- 8. Interim Analysis
- 9. Safety Analysis
- 10. Data Quality and Management
- 11. Software
- 12. Appendices

1. Introduction

• **Purpose of the SAP**: This document outlines the statistical approach for analyzing data from the clinical trial studying the effects of SGLT2 inhibitors on renal, cardiovascular, and hematological outcomes in lupus nephritis patients.

2. Study Design

Design: Randomized, double-blind, placebo-controlled clinical trial.

Study Duration: Conducted from September 2022 to November 2023

Randomization: Patients were randomly assigned to either dapagliflozin (10 mg once daily) or placebo groups using computer-generated random tables in a 1:1 ratio stratified by age and gender.

Blinding: The study was double-blinded, and all trial staff and participants remained unaware of individual treatment assignments until study completion.

3. Study Objectives

Primary Objective: To evaluate the impact of SGLT2 inhibitors on renal, cardiovascular, and hematological parameters in lupus nephritis patients.

Secondary Objective: To explore changes in body weight, BMI, and other echocardiographic and iron profile parameters over 12 months.

4. Endpoints

Primary Endpoints

Renal Function: Serum creatinine, eGFR, and 24-hour urine protein

Cardiovascular Health: BNP levels and coronary calcification via NCCT

Hematological Parameters: Hemoglobin and erythropoietin levels

Hepcidin Level: Measured before and after intervention

Secondary Endpoints

Body Weight and BMI: Assessed at baseline and follow-up visits.

Echocardiographic Findings: Assessed pre- and post-intervention.

Iron Profile: Serum ferritin and TSAT

5. Sample Size Justification

Calculation: A sample size of 100 patients was targeted, accounting for potential dropouts, to provide sufficient power (80%) at a significance level of 0.05 to detect differences between the two groups.

6. Statistical Methods

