
General Considerations

Significance Level: A two-sided alpha level of 0.05 will be used for all primary analyses.

Analysis Populations:

Intent-to-Treat (ITT): All randomized patients will be analyzed according to their assigned group.

Per-Protocol (PP): Only patients completing the study without major protocol violations.

Primary Endpoint Analysis

Renal Outcomes: ANOVA for repeated measures for serum creatinine and eGFR if normally distributed, and the Friedman test for non-normally distributed data. Post-hoc tests using Bonferroni correction.

Cardiovascular Outcomes: Mann-Whitney U test for BNP levels and coronary calcification between groups.

Hematological Outcomes: Paired t-test for hemoglobin and erythropoietin levels if data is normally distributed; otherwise, Wilcoxon signed-rank test.

Secondary Endpoint Analysis

Body Weight and BMI: Compared over time using ANOVA for repeated measures.

Echocardiographic Parameters: Analyzed with paired t-tests, adjusted with Bonferroni correction.

Iron Profile: Analyzed pre- and post-intervention using ANOVA or Kruskal-Wallis for non-normally distributed variables.

Categorical Variables

Chi-Square Test: For between-group comparisons of categorical data (e.g., presence of diabetes, hypertension).

7. Handling of Missing Data

Imputation: Last observation carried forward (LOCF) for data missing at random; multiple imputation for extensive missing data.

Sensitivity Analysis: Conducted to evaluate the robustness of primary endpoint findings against different missing data assumptions.

8. Interim Analysis

Timing: An interim analysis is planned at the halfway point (6 months).

Stopping Rules: An O'Brien-Fleming approach will be applied to adjust the significance threshold for interim testing, allowing for an earlier stop for efficacy or safety concerns.

9. Safety Analysis

Adverse Events (AEs): Summarized by type, frequency, and severity. Fisher's exact test will be used to compare AE rates between groups.

Specific Safety Parameters: Monitoring for hypotension, electrolyte imbalances, and kidney function.

10. Data Quality and Management

Data Quality Measures: Includes data verification, regular audits, and query resolution.

Database Lock: Data will be locked and verified prior to the final analysis.

11. Software

Statistical Software: All analyses will be conducted using SPSS (Version 25).

12. Appendices

	Control group. (n= 41)	Study group. (n= 38)	P value

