Age (years) Mean ± SD	36.6 ± 9.6	38±9.8	0.8
Sex No. (%) - Male - Female	7 (17.1%) 34 (82.9%)	4 (10.5%) 34 (89.5%)	0.5
Body weight (Kg) mean ± SD	78.9 ± 14	90 ± 15	0.5
Body mass index (Kg/m ²) mean ± SD	30.6 ± 10.5	33±5.7	0.6
Hypertension No. (%)	37 (90.2%)	38 (100%)	0.1
Diabetes No. (%)	7 (17.1%)	11 (28.9%)	0.2

Table (1): Demographics and associated medical disorders:

(Student T test or Mann-Whitney) for continuous data, and chi-square test for categorical data. Continuous data are expressed as mean (SD) or median (minimum – maximum). Categorical data are expressed as number (percentage), Level of significance < 0.05.

Table (2): SLE characteristics:

	Control group. (n= 41)	Study group. (n= 38)	P value
Disease duration (years) Median (min, max)	6 (1, 20)	7(1,19)	0.3

Lupus nephritis class No.			
(%)			
- Class I	1 (2.4%)	1 (2.6%)	
- Class II	2 (4.9%)	7 (18.4%)	0.1
- Class III	11 (26.8%)	8 (21.1%)	0.1
- Class IV	26 (36.4%)	16 (42.1%)	
- Class V	5 (2.4%)	1 (13.2%)	
- Class VI	0 (0%)	1 (2.6%)	
Activity index Median	6 (0, 10)	6 (0, 21)	0.8
(min, max)	0 (0, 19)	0 (0, 21)	0.8
Chronicity index Median	2(0, 8)	5 (0, 14)	0.2
(min, max)	2 (0, 8)	5 (0, 14)	0.2
Anti- phospholipid No.	6 (14 6%)	3 (7.0%)	0.4
(%)	0 (14.070)	5 (7.970)	0.4
Immunosuppressive			
medications No. (%)			
- Steroid + MMF	27 (65.9%)	18 (47 4%)	
- Steroid + CNI	5 (12.2 %)	4(10.5%)	0.2
- Steroid + CNI + MMF	2 (4.9 %)	1 (2 6%)	0.2
- Steroid + Azathioprine	7 (17.1%)	14(36.8%)	
- Steroid	0 (0%)	1 (2 6%)	
		1 (2.070)	
Cyclophosphamide No.	7 (17 1%)	5 (13.2%)	0.7
(%)	(1,11,0)		
Other medications No. (%)			
- Aspirin	15 (36.6%)	18 (34.4%)	0.3
- Statins	30 (73.2%)	24 (63.2%)	0.4
- Allopurinol	10 (24.4%)	14 (36.8%)	0.3
- ACEI/ARBS	26 (63.4%)	27(71.1%)	0.4
- Diuretics	14 (34.1%)	16 (32.1%)	0.3

MMF: mycophenolate mofetil; CNI: calcineurin inhibitors; ACEI/ARBS: angiotensin converting enzyme inhibitors/angiotensin receptor blockers; (Student T test or Mann-Whitney) for continuous data, and chi-square test for categorical data. Continuous data are expressed as mean (SD) or median (minimum – maximum). Categorical data are expressed as number (percentage).; Level of significance < 0.05.

	Control group. (n= 41)	Study group. (n= 38)	P value
Consumed C3 & C4 No. (%)	5 (12.2%)	2 (5.3%)	0.4

S. creatinine (mg/dL) Median (min, max)	0.8 (0.4, 2.7)	0.8 (0.4, 2.6)	0.8
24- hour urinary protein (g/24 hours) mean ± SD	0.4 (0.06-3.6)	0.6 (0.07-3)	0.3
eGFR (ml/min/m ²) mean ± SD	114 ± 51	128 ± 59.7	0.6

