Cholesterol mg/dL mean ± SD	185 ± 46	172 ± 40.7	0.5
Albumin (g/dL) mean ± SD	3.7 ± 0.4	3.7 ± 0.3	0.4
Random blood sugar (mg/dL) Median (min, max)	89 (66, 568)	92.5 (64, 243)	0.4
Uric acid (mg/dL) mean ± SD	6.2 ± 2.1	6.5 ± 1.7	0.2
Alanine aminotransferase (IU/L) Median (min, max)	17 (2, 84)	17 (7, 82)	0.8
Aspartate aminotransferase (IU/L) Median (min, max)	21(9, 66)	19 (12,72)	0.4
Sodium (mEq/L) mean ± SD	137 ± 3.1	136 ± 3	0.5
Potassium (mEq/L) mean ± SD	3.9 ± 0.4	4 ± 0.4	0.3

eGFR: estimated glomerular filtration rate; (Student T test or Mann-Whitney) for continuous data, and chisquare test for categorical data. Continuous data are expressed as mean (SD) or median (minimum – maximum). Categorical data are expressed as number (percentage). Level of significance < 0.05.

Table (4): Baseline hematological findings:

	Control group. (n= 41)	Study group. (n= 38)	P value		
Hemoglobin (g/dL) Mean \pm SD	11.9 ± 1.9	11.7 ± 1.7	0.5		
MCV (FL) Mean ± SD	82 ± 7	84 ± 6.9	0.9		
MCH (Pg) Mean ± SD	25.4 ± 2.9	26.3 ± 2.9	0.9		
Ferritin (mg/dL) Median (min, max)	60 (13, 1113)	33.5 (3, 1460)	0.09		
TSAT (%) Median (min, max)	23.8 (7, 64)	18 (6, 74)	0.05		
Erythropoietin level (IU/L) Mean ± SD	11.6 ± 2.1	11.3 ± 1.4	0.1		
Hepcidinlevel(ug/L) $Mean \pm SD$	198 ± 74	182 ± 76	0.3		
Platelet count (*10 ³) Mean \pm SD	288 ± 71	300 ± 79	0.7		

McW Mean corpuscle volume; MCH: Mean corpuscular hemoglobin; TSAT: Transferrin saturation test; (Student T test or Mann-Whitney) for continuous data, and chi-square test for categorical data. Continuous data are expressed as mean (SD) or median (minimum – maximum). Categorical data are expressed as number (percentage).; Level of significance < 0.05.

Table (5): Baseline Cardiac evaluation:

Control group. Study group. P value

	(n= 41)	(n= 38)	
Coronary calcification No. (%)	3 (7.3%)	11 (28.9%)	0.012
Coronary calcification severity No. (%) - No - Minimal - Mild - moderate	38 (92.7%) 1 (2.4%) 1 (2.4%) 1 (2.4%)	27 (71.1%) 3 (7.9%) 7 (18.4%) 1 (2.6%)	0.04
BNP (ng/L) Median (min, max)	52 (40, 557)	52 (34, 90)	0.8
Echocardiographic	c finding		0.6
EF % Mean \pm SD	65.4 ± 9.3	64.6 ± 5.4	0.6
LAD (ml) Mean ± SD	24.2 ± 7.6	24.9 ± 7.6	0.6
Aortic diameter (ml) Mean ± SD	24.7±7.4	24.8±7.1	0.9
ESV (ml/m) Median (min, max)	38±13.6	41±13.9	0.4
EDV (ml/m) Mean ± SD	98±35.7	111.5±31.6	0.08

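### The primary haematological endpoints have no planned between-arm test, and the arm comparisons that are shown leave lower baseline iron in the study arm unadjusted

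*SAP*

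**What the plan says.** - **Endpoints.** SAP section 4 lists "Hematological Parameters: Hemoglobin and erythropoietin levels" as primary and hepcidin as a further primary item. Ferritin and TSAT are secondary.
- **Question.** The primary objective in SAP section 3 is the impact of the drug. The sample size in SAP section 5 is meant "to provide sufficient power (80%) at a significance level of 0.05 to detect differences between the two groups".
- **Planned test.** SAP section 6 gives "Hematological Outcomes: Paired t-test for hemoglobin and erythropoietin levels if data is normally distributed", with the Wilcoxon signed-rank test otherwise. It names no test for hepcidin. The iron profile is analysed as an outcome in its own right, not as a covariate.
- **Randomisation.** SAP section 2 stratifies by age and gender only.
- **Baseline iron.** In Table 4 the row "TSAT (%) Median (min, max") shows 23.8 (7, 64) in control and 18 (6, 74) in the study arm, p=0.05. Ferritin is 60 (13, 1113) and 33.5 (3, 1460), p=0.09.
- **Comparisons shown.** The footnotes to Tables 7 and 8 give a t-test or Mann-Whitney test between arms. Figure 3 compares anaemia: "the drug group has 16 participants (42.1%), while the placebo group has 22 participants (53.7%)".
- **Concomitant treatment.** The Table 2 block "Other medications No" covers aspirin, statins, allopurinol, ACEI/ARBs and diuretics. Iron, ESA and transfusion appear neither there nor in Table 10, nor in the protocol's eligibility criteria or data lists.

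**The concern.** There are two linked gaps. First, the question is drug against placebo, but the test named for two of the three primary haematological endpoints looks only at change within an arm, and the third endpoint has no test. The between-arm p-values in the appendix therefore do not come from any analysis specified for these endpoints in section 6.

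Second, those between-arm comparisons use raw values although the study arm started with lower TSAT and ferritin. About 60% of each arm was anaemic at baseline (23/38 and 24/41), so iron status may well matter for haemoglobin. Baseline haemoglobin is nearly equal (11.7 v 11.9 in Table 4), so adjusting for it alone would not remove an iron imbalance. Treatment that acts directly on these endpoints is unreported, so the reader cannot see whether it differed by arm. At stake is the interpretation of the estimated haematological difference, in either direction.

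**Working it through.** **1. What a paired test delivers here.** Table 8 applies one to hepcidin. Control falls from 198 to 128 (p=0.001) and study from 182 to 116 (p=0.001). Both arms are significant, including placebo. The changes are -70 and -66, so the arms differ in mean change by only 4. The within-arm p-values say nothing about the drug.

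**2. Reproducing the printed between-arm p-values** (means, SDs or counts from Table 8, Table 7 and Figure 3; n=41 and 38):

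| Comparison | Study minus control | Recomputed p | Printed p |
|---|---|---|---|
| Haemoglobin, 12 months | 12.0 - 12.2 = -0.2 | 0.65 | 0.6 |
| Erythropoietin, 12 months | 12.4 - 12.8 = -0.4 | 0.61 | 0.6 |
| Hepcidin, 12 months | 116 - 128 = -12 | 0.26 (Welch 0.24) | 0.2 |
| Anaemia, baseline | 23/38 v 24/41 | 0.857 | 0.857 |
| Anaemia, post | 16/38 v 22/41 | 0.30 | 0.3 |

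These agree closely enough to confirm that the comparisons are unadjusted. For haemoglobin, SE = sqrt(1.9²/41 + 2²/38) = 0.44, and the 95% CI is -1.07 to +0.67.

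**3. Size of the iron imbalance.** The TSAT and ferritin p-values cannot be recomputed from medians and ranges, so I worked back from them: d = t(p, 77 df) × sqrt(1/41 + 1/38).
- TSAT, p=0.05: 1.991 × 0.225 = 0.45 SD.
- Ferritin, p=0.09: 1.717 × 0.225 = 0.39 SD.

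A rank-based conversion gives 0.46 and 0.40.

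**4. Effect on the haemoglobin difference.** Shift = slope × d × SD, with d = 0.45 and SD = 1.95 (midway between 1.9 and 2.0). The standardised slope r of 12-month haemoglobin on baseline iron is an assumption. Adjusted SE = SD × sqrt(1/41 + 1/38) × sqrt(1 - r²) × sqrt(1 + d²/4).

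| Assumed slope | Shift (g/dL) | Adjusted difference | p |
|---|---|---|---|
| 0.1 | 0.09 | -0.11 | 0.80 |
| 0.2 | 0.18 | -0.02 | 0.96 |
| 0.3 | 0.26 | +0.06 | 0.88 |
| 0.4 | 0.35 | +0.15 | 0.72 |

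The sign changes once the slope passes 0.2/(0.45 × 1.95) = 0.23. With d = 0.39 the p-values stay between 0.78 and 0.95.

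**5. The other endpoints, and the opposite sign** (slopes 0.1 to 0.4 in absolute value, d 0.39 to 0.45). The documents do not fix the sign of the slope, so both are shown.

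| Outcome | Positive slope | Negative slope |
|---|---|---|
| Haemoglobin | -0.12 to +0.15, p 0.72 to 0.96 | -0.28 to -0.55, p 0.54 to 0.19 |
| Erythropoietin | -0.26 to +0.23, p 0.74 to 0.99 | -0.54 to -1.03, p 0.50 to 0.17 |
| Hepcidin (pooled SD 46.6) | -10.2 to -3.6, p 0.34 to 0.71 | -13.8 to -20.4, p 0.20 to 0.04 |

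Only hepcidin, at a negative slope near 0.4, reaches about p=0.05.

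**6. Own baseline.** The study-arm baseline haemoglobin is 11.7 in Table 4 but 11.8 in Table 7; control is 11.9 in both. The mean changes are therefore +0.3 or +0.2 in the study arm and +0.3 in control, a difference of 0 or -0.1. Most or all of the -0.2 was present at the start.

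**7. Iron markers at 12 months (Table 8).** Study TSAT goes from 18 to 20 (p=0.9) and ferritin from 33.5 to 64 (p=0.8). Control TSAT goes from 23.8 to 28 (p=0.1) and ferritin from 60 to 75 (p=0.5). The gap in median TSAT is 5.8 at baseline and 8 at 12 months.

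**The case against.** The arms were randomised, which promises balance in expectation, not in every marker. Tables 1 to 5 hold about 45 baseline tests, so two related markers at p=0.05 and 0.09 are unremarkable. Covariates picked because of those p-values are data-driven. The slope is assumed, and the resulting shift lies well inside a confidence interval with half-width 0.87 g/dL. All of this stands. It is why the iron-adjusted result should be labelled and shown beside the unadjusted one, and why own-baseline adjustment comes first. None of it supplies the missing between-arm analysis.

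Three stronger readings are tempting, and the documents do not support them.

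- **A reader might infer that the planned tests are themselves distorted by the imbalance.** Section 6 plans within-patient tests, which do not compare the arms. The imbalance bears on Tables 7 and 8 and Figure 3.
- **A reader might infer that drug and iron effects cannot be separated, or that the iron data go unused.** Baseline TSAT and ferritin are recorded, can be adjusted for, and are analysed as secondary endpoints. Inseparability is arguable only for iron, ESA or transfusion given during follow-up.
- **A reader might infer that iron was given more often in the study arm and explains its fall in anaemia from 23 to 16.** The study ferritin median rose, but neither within-arm test shows a change and the TSAT gap did not close. Nor does silence show that such treatment went unrecorded: the protocol's data lists also omit aspirin, statins and allopurinol, which Table 2 reports. Only non-reporting is established.

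**Conclusion.** The point holds as a gap in the analysis specification. The firm part needs no assumption: two primary haematological endpoints have only a within-arm test, hepcidin has none, and no primary haematological analysis adjusts for baseline iron. The size of the iron effect is conditional. At an assumed slope of 0.1 to 0.4 it is about 0.09 to 0.35 g/dL against a raw difference of -0.2 g/dL. That changes the sign above a slope of about 0.23 and leaves the result non-significant if higher iron goes with higher haemoglobin. Exact adjusted values need patient-level data. The gain is an interpretable estimate and interval for drug against placebo; a new significant finding should not be expected.

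**What to change.** In SAP section 6:

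1. Replace the paired tests with a between-arm model for 12-month haemoglobin, erythropoietin and hepcidin, containing arm and the outcome's own baseline value.
2. Add baseline TSAT and/or log ferritin in a second, labelled adjusted analysis, stating that these covariates were chosen after the imbalance was seen.
3. Report the arm difference with its 95% CI from both models, beside the unadjusted difference. Treat the Figure 3 anaemia comparison the same way, and reconcile the two baseline haemoglobin values (11.7 and 11.8).
4. From existing files, report iron, ESA and transfusion use by arm, at baseline and during the 12 months. If this cannot be recovered, state that an effect of such treatment during follow-up cannot be excluded.

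Do not add an analysis that leaves out patients who started iron, ESA or transfusion. It would condition on an event after randomisation that the treatment may itself affect.

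The cost is SAP wording, two or three degrees of freedom out of 79 patients (one for the own baseline, one or two for iron) and a chart extraction. No new patients, visits or tests are needed.
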